#### **The impact of attrition.**

It is anticipated that some attrition will occur in this population, though we do not anticipate differential attrition by condition. A conservative estimate of 20% attrition over the course of data collection is assumed. Recently published evidence suggests an attrition rate of approximately 20% for other trials. In our own previous trials, we have seen attrition of around 20%. Thus, sample size will need to be increased by 20% over minimum requirements. After final attrition has been calculated, pretest differences on alcohol use and problems will be compared among individuals who finished the study versus those who did not and by condition, to determine whether these two groups differed in

systematic ways and whether these differences were related to treatment condition.

With respect to attrition during the follow-up period, all participants will update their address and phone number as well as the name and number of an individual who always knows how to reach them at every visit. The project coordinator will also contact each patient in between follow-up visits.

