### **Baseline Session**

After arriving at the lab, qualified participants will (1) complete an informed consent form, and then (at either the same session or a separate session), participants will (2) complete a breath alcohol test, (3) complete a urine toxicology screen, (4) provide a blood sample for assays of peripheral inflammatory markers and DNA methylation, (5) fill out the baseline questionnaires, (6) and take several neurocognitive tasks. Participants will also be given a gut microbiome sample collection kit at the end of the session and will return it to their first scheduled session (7).

Subjects will be breathalyzed before every session starts, including all therapy sessions. Any subject that has a positive BAL or who reports drinking will be rescheduled for that appointment. A participant who blows a BAC over 0.00 will be given one chance to reschedule his/her appointment for the next day. If s/he comes in the next day with a breath alcohol greater than 0.00 then this session will be counted as “missed.” If a subject accumulates more than one “missed” session, they will be automatically dropped from the study on the grounds that they failed to follow explicit study directions properly. Participants will not receive compensation if a session is terminated due to failure to follow the abstinence instructions. They will be informed of this contingency during the phone screen, consent visit and is stated the consent form.

A urine toxicology screen will be administered to insure that subjects have not recently used illicit drugs including, sedatives, opiates, cocaine, or amphetamines.

A member of our research team who has completed a certified training in phlebotomy will collect the blood sample. The blood draw procedures will involve collecting venous blood (40 ml) venipuncture of a peripheral arm vein using standard, sterile phlebotomy techniques. The samples will be tested for cytokine levels and epigenetics using equipment at the CINC.

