### **Check-in Session (33 weeks)**

Those subjects who participated in the MRI scan will return for a visit with a therapist one week after their second follow-up session. Before this session starts, participants will take a BAC test. During this session, the therapist will assess whether there were any adverse events, including lapses that may have resulted from the alcohol cues administered during the MR scan. Any adverse events will be addressed in the session and reported to the PI. At the end of their last session (33 weeks), participation in the study is complete.

Name of instrument/tool/procedure	Purpose (i.e. what data is being collected?)	Time to Complete
Questionnaire Measures Collected at Baseline Only		10 minutes
Demographics	

• A demographics questionnaire will be used to collect information on age, sex, marital status, SES, occupation, income, education, and race.

	
The Stages of Change Readiness and Treatment Eagerness Scale (SOCRATES)	

• SOCRATES (Miller & Tonigan, 1996) is an experimental instrument designed to assess readiness for change in alcohol abusers. The instrument yields three factorially-derived scale scores: Recognition (Re), Ambivalence (Am), and Taking Steps (Ts). It will be used to measure individual differences in motivation at baseline.

	

---

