### **Exposure to Alcohol.**

During the fMRI scan at baseline and the second follow-up visit, participants are exposed to less than a teaspoon of an alcoholic beverage, there is a risk that participants may experience an urge to drink or it might cause cravings or anxiety. This risk is particularly relevant during the second MRI scan because many patients may have established abstinence or reduced their alcohol consumption substantially.

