### **Exposure to Alcohol.**

During the fMRI session, participants may experience a reaction to the alcohol presented to them during the scan. Such a reaction might manifest as craving or anxiety. These effects are almost always only temporary. We have used the same cue exposure task in over 600 participants; many of who were treatment-seeking patients who had established some measure of abstinence (required to be in our studies) prior to scanning. We have not observed any adverse effects from our cue exposure protocol in these individuals. It is important to understand that the entire task uses less than 1 tsp of an alcohol beverage. The consent form clearly notes that the cue exposure session takes place at baseline and at the second follow-up session (week-32) and clearly notes that patients can opt out of the cue exposure part of the study. The patients will be reminded again about the option to opt out of the MR scan. As we have done previously, we will conduct an assessment with each participant after the cue exposure session to determine whether there is any residual craving or anxiety. We also allow each patient to process his or her reaction to the alcohol cues with a therapist before leaving the experiment. Thus, the therapist and study staff will know immediately if there is an adverse reaction to the cues. The therapist will address any adverse reactions to the cues at that time. In addition, therapists will now see all patients for an additional week of therapy. Thus, a plan is also in place for follow-up with these patients. During this session at week-33, the therapist will assess whether there were any adverse events, including a lapse that may have resulted from the cues. Any adverse events will be addressed in the session and reported to the PI. These procedures ensure that the patient does not leave the lab in a vulnerable state. If more than five individuals during the entire trial report having a lapse within 48 hours of the cue exposure session, we will discontinue the cue exposure assessment.

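### The breath-test rule can cancel the week-33 visit meant to find lapses after the cue scan, and the protocol does not say how the lapses of patients turned away are obtained or counted

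*Combined protocol and SAP*

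**What the plan says.** The breath-test rule is printed in section XI under Baseline Session, but its scope is general: "Subjects will be breathalyzed before every session starts, including all therapy sessions". The consequence is "Any subject that has a positive BAL or who reports drinking will be rescheduled for that appointment". For a positive reading the text continues: "A participant who blows a BAC over 0.00 will be given one chance to reschedule his/her appointment for the next day". A second positive on that next day makes the session a missed one, and more than one missed session removes the participant from the study.

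Under Check-in Session (33 weeks), scanned participants return to a therapist one week after the week-32 visit. The protocol says "Before this session starts, participants will take a BAC test", and the section XI visit table also lists a BAC test for this visit. The purpose is stated there: "During this session, the therapist will assess whether there were any adverse events, including lapses that may have resulted from the alcohol cues". Section XVI, Exposure to Alcohol, repeats it: "During this session at week-33, the therapist will assess whether there were any adverse events, including a lapse that may have resulted from the cues". Events found are to be reported to the PI. The same paragraph of section XVI sets the discontinuation rule: cue exposure ends if more than five individuals over the whole trial report a lapse within 48 hours of the cue session.

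**The concern.** At this one visit, drinking is both the event being looked for and a reason for not holding the appointment. The two instructions were written for different purposes, and no sentence says which prevails at week 33.

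What is at stake is the information feeding a participant-safety rule. Lapses that go unasked or unrecorded do not enter the count, and the cue exposure could continue after the protocol's own limit had in fact been passed. A patient who was turned away could also look, in a safety report, the same as one who had no event.

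**Working it through.** The plan gives no figure to reproduce here. The check is mainly a reading of the rules together, followed by simple arithmetic on the threshold.

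**Step 1. Does the rule reach week 33?** Baseline Session covers every session. Check-in Session (33 weeks) and the visit table both put a BAC test at that visit. No exemption appears in section XI, XVI or XVIII. So yes, as written.

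**Step 2. What happens at the door?** Following the text exactly:

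| Patient at week 33 | What the text does | Lapse enquiry |
|---|---|---|
| Breath test 0.00, no drinking reported | Session held | Made |
| Positive, then 0.00 the next day | Rescheduled, then held | Made one day late |
| Positive on both days | Session counted as missed | Not provided for |
| Positive, does not return | Rescheduled, not held | Not provided for |
| Breath test 0.00 but reports drinking | Rescheduled; no look-back period, deadline or missed label given | Depends on the meaning of reported drinking and on return |

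The enquiry is clearly at risk in the third and fourth rows. The fifth row is undefined.

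**Step 3. Is there another scheduled look after the second scan?** The therapist's assessment on the scan day takes place before the patient leaves, so it cannot see a later lapse. The Timeline Follow Back is last collected at week 32, the same visit as the scan. The attrition section says "The project coordinator will also contact each patient in between follow-up visits", but week 32 is the last follow-up visit, so those contacts do not fall after it. The week-33 visit is the only scheduled enquiry covering the 48 hours after the second scan.

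**Step 4. How sensitive is the rule to lost reports?** More than five means at least 6 reports. With T true lapses within 48 hours, the rule stays silent if at least T − 5 of them go unrecorded:

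- T = 6: 6 − 5 = 1 unrecorded lapse is enough.
- T = 8: 8 − 5 = 3 unrecorded lapses are enough.

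As an illustration only, suppose each true lapse is recorded independently with probability q. Then P(rule triggers) = P(Binomial(T, q) ≥ 6). Both T and q are assumptions, because the documents give neither.

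| q (assumed) | T = 6 | T = 8 |
|---|---|---|
| 0.9 | 0.53 | 0.96 |
| 0.7 | 0.12 | 0.55 |
| 0.5 | 0.02 | 0.14 |
| 0.3 | 0.001 | 0.01 |

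For example, at T = 8 and q = 0.5 the result is (28 + 8 + 1)/256 = 37/256 = 0.14. The table shows how a low count threshold behaves. It does not estimate what this trial would lose.

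**The case against.** The strongest reply is that few patients would be lost. The retry and the missed label apply only to a reading above 0.00. Losing the enquiry through the breath test therefore takes two positive days or a failure to return. The lapses that count occur within 48 hours of the scan, and the check-in is a week later. A patient who lapsed and then stopped would normally arrive sober and be seen. There are also general routes. Section XVIII requires adverse events to reach the PI immediately and has the DSMB review them every three months. The count in section XVI is of people who report a lapse, with no restriction to the week-33 session. This stands and narrows the point, but none of it says that a patient turned away is asked, recorded or counted.

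A reader might infer several stronger things that the documents do not support:

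- *Any admitted drinking cancels the visit.* The rule gives no look-back period. It sits beside the abstinence instructions, which are given as 48 hours for the baseline session. Abstinence is encouraged but not required, and drinking is collected at every assessment.
- *Under-recording rises in proportion to how badly patients do.* Nothing in the documents establishes that relation.
- *The baseline scan needs the same check-in.* Section XV does say "During the fMRI scan at baseline and the second follow-up visit, participants are exposed to less than a teaspoon of an alcoholic beverage", but it goes on to call the risk particularly relevant at the second scan, when many may be abstinent or drinking much less. Baseline patients are recent heavy drinkers who go on to a goal-setting session and weekly therapy.
- *Section XVI contradicts section XI on who attends week 33.* Its reference to all patients is in a paragraph about people exposed to the cues and can be read as the scanned patients.
- *The lack of a listed payment for week 33 is an error.* That is a design preference.

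**Conclusion.** The point holds in a limited form. The breath-test rule and the week-33 lapse enquiry conflict as written. Following both exactly can leave a scanned patient who is still drinking at week 33 without any lapse enquiry, and with no stated route into the discontinuation count.

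The size of the under-count cannot be derived, because the documents give no number scanned at week 32, no expected lapse rate and no capture rate. The section on exposure to alcohol reports no adverse effects with the same task in over 600 participants, so true lapses may be few. What can be said is that the threshold is six reports and that, near it, one to three lost reports are enough to keep the rule silent.

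The conclusion assumes that the every-session wording means what it says and that no operating procedure outside these documents exempts week 33. It is confined to the in-person MRI subset; the remote version has no scan and no week-33 visit.

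**What to change.** Reconcile Baseline Session with Check-in Session (33 weeks), the section XI visit table and section XVI, Exposure to Alcohol, so that the protocol states:

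1. whether the reschedule and missed-session rule applies to the week-33 check-in, and what period reported drinking refers to there;
2. how lapse information is obtained for a scanned patient who is rescheduled or recorded as missed, how it reaches the PI, and how it enters the discontinuation count;
3. that scanned patients with no week-33 lapse information are reported to the DSMB as unknown, not as having had no event.

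The clinical rule for a patient with a positive breath test is for the investigators to settle. The point here is only that the passages must agree and the count must be complete.

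The cost is protocol wording, slightly more follow-up and recording work, and some answers given by people who have been drinking. Sample size and analysis are unaffected.

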#### ***Data Analysis Plan:***

Analyses will be conducted using SAS Version 9.3 and EQS for Windows Version 5.7b. We will conduct extensive analyses of any attrition encountered in the project to determine bias. However, note that in each of the analyses described herein, we will have the capability of using modern approaches to the handling of missing data (Schafer & Graham, 2002) including full information maximum likelihood (FIML) estimation of missing data within Proc Mixed in SAS and within EQS.

Descriptive analyses. The distributional properties of all continuously scaled variables will be examined for skewness and kurtosis to determine the need for normalizing transformations or for alternations to our analysis plan (i.e., generalized estimating equations in SAS or robust estimation in EQS) prior to the primary analyses.

Pretest equivalence. To confirm the validity of random assignment, pretest equivalence of the two treatment conditions across demographics, drinking history, smoking, and all other baseline measures will be assessed via t-tests on continuous items and  $\chi^2$  tests of categorical items. We will use the Bonferroni approach (Keppel, 1991) to correct for alpha inflation with a familywise alpha of .05. Any variables on which the two groups are unequal at pretest will be covariates in all further analyses.

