#### **Specific Aim 1 - Detecting Treatment Effects on Drinking Outcomes.**

The effect of the treatment on alcohol use outcomes (HYPOTHESIS 1) will be analyzed with a 2 (**Treatment:** 8 weeks of MBRP vs. 8 weeks of RP) x 5 (**Time:** Baseline, 4, 8, 20, 32 weeks) mixed general linear model with Heavy Drinking Days (HDD) as the primary outcome variable. We will also examine drinks per drinking day, ICS score, and liver function tests as dependent measures in each of 2 additional models, respectively. In the main analysis with HDD, a significant overall test of the treatment X time interaction will be followed by planned contrasts within the mixed model that allow us to test the superiority of MBRP over RP at the 8, 20, and 32 week follow-up points specifically. The FIML estimation procedure implemented in these analyses will allow us to utilize an “intent to treat” approach such that all subjects who are randomized will be included in the analyses (Schafer & Graham, 2002). It may be that the treatments are equally effective on drinking outcomes, and thus we will not see a direct effect of treatment on outcomes. Even in this case, it is possible that the mechanisms through which the treatments had their impact may differ. Thus, tests of Specific Aims 2 and 3 are still important and warranted.

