### **Differential attrition analyses.**

Attrition analyses will be conducted after each follow-up data collection effort to provide assurance that differential attrition by treatment condition has not occurred. Following previously published procedures (Jurs & Glass, 1971), a series of ANOVAs of treatment (MBRP versus RP) X retention (retained, not retained) will be conducted on continuous baseline measures. Significant treatment X retention interactions identify measured variables on which differential attrition may have occurred. The logit model analog procedure will be applied to categorical baseline measures to test for differential attrition on categorical variables such as gender and ethnicity (Agresti, 1990). We will conduct these analyses to assure that differential attrition by treatment condition does not account for any of the effects of the treatments.

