**Questionnaire Measures**  
**Collected at Baseline, 4, 8, 20,**  
**32 weeks**

**Timeline Follow Back (TLFB)**

- The TLFB (Sobell, Maisto, Sobell, & Cooper, 1979) is an assessment method that obtains estimates of daily alcohol, cigarette, and drug use. The TLFB has been shown to have good psychometric characteristics with a variety of drinker groups and can generate variables that provide a wide range of information about an individual's drinking (e.g., pattern, variability, and magnitude of drinking). This instrument requires subjects to recall from memory the number of drinks consumed for each day over the prior 30 days as well as their use of tobacco products and recreational drugs. Studies with alcoholics have shown this instrument to be reliable in assessing drinking frequencies and other behaviors such as arrests and hospitalizations (Sobell et al., 1979).

---

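### In-person participants removed for repeated alcohol-positive breath tests have no stated follow-up for heavy drinking days, and no planned analysis examines what their missing outcomes could do

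*Combined protocol and SAP*

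**What the plan says.** **The removal rule (Section XI, Baseline Session).** In-person participants are breath-tested before every session, therapy sessions included. A positive test earns one rescheduled appointment the next day: "If s/he comes in the next day with a breath alcohol greater than 0.00 then this session will be counted as" missed. With more than one such session, "they will be automatically dropped from the study on the grounds that they failed to follow explicit study directions properly". The removal is from the study, not only from treatment.

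**Follow-up.** The sections on the 20- and 32-week assessments say that all subjects complete the self-report measures, and offer an online survey to those who cannot come to the laboratory. Neither mentions participants already removed. The remote (COVID-19) procedures list no breath test, so the rule concerns in-person participants.

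**Outcome.** HDD comes from the Timeline Follow Back, in which participants "recall from memory the number of drinks consumed for each day over the prior 30 days".

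**Analysis.** The Data Analysis Plan relies on "full information maximum likelihood (FIML) estimation of missing data within Proc Mixed in SAS", and the Aim 1 section says that "all subjects who are randomized will be included in the analyses". On attrition:
- The Data Analysis Plan promises in general terms: "We will conduct extensive analyses of any attrition encountered in the project to determine bias".
- The impact of attrition: "pretest differences on alcohol use and problems will be compared among individuals who finished the study versus those who did not and by condition".
- Differential attrition analyses: "a series of ANOVAs of treatment (MBRP versus RP) X retention (retained, not retained) will be conducted on continuous baseline measures", with a logit analogue for categorical baseline measures.

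**Expected frequency.** Section XIV treats withdrawal without consent, including for plainly not following instructions, as very unlikely.

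**The concern.** The event that ends participation is current drinking, and the primary outcome is a count of heavy drinking days. If HDD collection stops at removal, the value lost is related to the reason it was lost. Likelihood estimation keeps every earlier observation, but fills the gap as if later drinking were predictable from what was recorded before. The plan neither states nor defends that missing-at-random assumption.

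The specified attrition tests look only at characteristics measured before treatment. Two arms can match perfectly on those and still differ in drinking after randomisation, so the tests cannot give the assurance the differential-attrition section wants from them. At stake is whether a reader of the HDD result can judge how far it depends on an assumption that the protocol's own rule puts in doubt.

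**Working it through.** **1. The plan's own figures.** Inputs from the Aim 1 power section: f = .10, 5 assessments, correlation .50, N = 180, two-sided alpha .05. Noncentrality = f² × N × 5 / (1 − .50) = .01 × 180 × 5 / .50 = 18, with 4 and 4 × 178 = 712 degrees of freedom. Power is .942, which agrees with the stated figure of well over .90. For attrition, 180 / (1 − .20) = 225, against about 226 stated. Nothing below changes these.

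**2. How many positive tests removal takes.** Two missed sessions, each needing a positive test on the day and another the next day: 2 × 2 = 4 positive readings.

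**3. Which recall windows can contain the triggering drinking.** Weeks 0 to 4 and 4 to 8 are each 4 × 7 = 28 days, inside the 30-day recall. A removal during treatment therefore falls in the window of the next planned assessment. The week-20 window reaches back 30 / 7 = 4.3 weeks, to about week 15.7, so it misses anything that happened by week 8. The drinking-related loss sits mainly in the first assessment after removal. Later assessments are affected only as far as drinking persists.

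**4. What each planned check can see.**
- Completers against non-completers: pretest alcohol use and problems only.
- Treatment-by-retention tests: baseline measures only.
- The general promise of attrition analyses: no method named.
- Delta-adjusted, pattern-mixture, selection-model, worst-case or tipping-point analysis of HDD: none found.

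**5. Size.** The documents give no removal rate, so all rates here are assumptions. Both simulations use five visits with correlation .50, the MBRP effect at d/2 at week 4 and d afterwards, the same removal rule in both arms, and maximum likelihood under missing at random.

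*Simulation A* (150,000 per arm, d = .23). There are 11 breath-tested sessions after randomisation: goal-setting, eight weekly, weeks 20 and 32. The chance of a missed session is logistic in the current trigger (slope 1 or 2 per SD), and the trigger correlates 1 or .5 with drinking. Removal comes at the second miss. With about 5 to 10% removed, the effect is understated as follows:

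| Trigger correlation | Week 8 | Weeks 20–32 |
|---|---|---|
| 1 | .006 to .020 SD | .003 to .012 SD |
| .5 | .002 to .005 SD | .001 to .005 SD |

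Between 59 and 72% of those removed pass week 4 first, and each removed participant loses 2.88 to 3.13 of the four later assessments.

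*Simulation B* (113 per arm, 300 replicates, Monte Carlo error about .008). A participant is removed when the unobserved week-4 or week-8 value exceeds a fixed threshold, which is a harsher rule.

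| True d | Removed RP / MBRP | Week-8 estimate | Shortfall |
|---|---|---|---|
| 0 | 13.6% / 13.8% | −.004 | none beyond error |
| 0 | 8.1% / 8.1% | .002 | none beyond error |
| .20 | 13.6% / 10.7% | .171 | .029 |
| .20 | 8.0% / 6.1% | .174 | .026 |

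The shortfall grows with the effect: at d = .40 the estimates are .331 and .369.

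**6. Against the standard error.** With 90 per arm, SE = √(2/90) = .149 SD. The range at d of about .2 is then .002/.149 = .01 SE to .029/.149 = .19 SE.

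**7. What a sensitivity analysis would move.** Shift in an arm's mean = share missing × delta. If 8% of one arm were missing at week 8 for this reason (assumed), deltas of .25, .5 and 1 SD in that arm move the difference by .02, .04 and .08 SD. With equal shares and equal deltas in both arms the shift is zero.

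**The case against.** The strongest reply is that the gap is inferred. No sentence forbids surveying removed participants, the follow-up sections speak of all subjects, the analysis includes everyone randomised, and the Data Analysis Plan promises to study attrition. All of that is true. It still leaves staff to decide what being dropped from the study means for the week-8, 20 and 32 questionnaires, and it names no analysis that could detect dependence on drinking after randomisation.

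The second reply is that the effect is small and rare. Four positive readings are needed, Section XIV expects withdrawals of this kind to be very unlikely, and a breath reading above zero is a noisy proxy for a 30-day count of heavy drinking days. This stands, and it is why the severity is low.

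Stronger readings are tempting but not supported:
- *Removed participants leave the analysis.* They do not. Their earlier HDD values stay in the likelihood.
- *The rule could create a treatment effect.* That needs it to act differently in the two arms. With 15% removed in one arm and 5% in the other, Simulation A's model gives .02 to .06 SD at week 8. The largest case, .064/.149 = .43 SE, would raise a 5% test to about 7%. The documents give no ground for such an imbalance. Both arms share the rule and session format, therapists are cross-trained, and differential attrition is not anticipated. Fifteen per cent from this rule alone would use 15/20, or three-quarters, of the attrition allowance for all causes.
- *All 226 participants are exposed.* Only those seen in person are, and the documents do not say how many that is.

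**Conclusion.** The point holds at low severity. For in-person participants the protocol removes people because of drinking, does not say that HDD is collected afterwards, relies on an unstated missing-at-random assumption, and specifies only attrition checks that cannot test it.

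Under a common rule with an assumed 5 to 14% removed per arm, the bias is toward the null and modest: about .002 to .03 SD at week 8 for an effect near .2 SD, and about zero with no true effect. The width of that range reflects the assumed mechanism, so the third decimals carry no weight. The actual size cannot be found from the documents. A larger bias would need unequal removal between arms, which the plan does not anticipate. Nothing here calls the sample size or the attendance rule into question.

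**What to change.** 1. Leave the attendance rule to the sponsor and separate it from outcome follow-up by adding: *Alcohol-related removal from sessions does not end outcome follow-up; every randomised participant stays on the TLFB/questionnaire schedule at weeks 4, 8, 20 and 32 unless they withdraw consent for it.* The online surveys offered at weeks 20 and 32 can serve. Weeks 4 and 8 would use an emailed link, as the remote procedures already do.
2. Report alcohol-related removals by arm and week.
3. Prespecify one delta-adjusted (tipping-point) sensitivity analysis for HDD still missing after such removal, with delta applied equally in both arms and then in each arm alone. State the delta at which the conclusion changes. A grid of 0, .25, .5 and 1 baseline SD would do; the choice is the trial statistician's.

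**Cost.** Section VIII pays $30 for surveys at weeks 20 and 32. At that rate the most is 4 × $30 = $120 per removed in-person participant. At the simulated 2.88 to 3.13 assessments lost, it is about $86 to $94. Add one extra analysis and matching changes to the consent form, phone screen and IRB submission, because participants are told of the removal rule at screening and consent.

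Separately, and with no bearing on the severity above, the payment statements must be reconciled. The weekly-sessions section withholds pay for therapy sessions already attended, while Section XIV provides prorated payment on early withdrawal.
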